All patients being treated with open reduction internal fixation for foot, ankle, tibia, elbow, forearm and wrist fractures at New York University Medical Center, NYU-Hospital for Joint Diseases will be asked to participate in this study. At the patients preoperative office visit, they will be asked to participate in the study and provided a copy of the consent form at that time which they can take home with them. All questions will be answered and they will be asked verbally if they will consent to being a part of the study. Patients will then have the opportunity to either sign the written consent forms or wait till the surgical date to think about the study and any additional questions they may have. At the time of surgery, patients will be consented for surgery. If the patient did not give written consent at the preoperative visit, they will be asked if they have any questions about the study. All questions will again be answered. They will then be asked verbally if they are willing to participate in the study, if they respond yes, then written consent will be obtained at that time.

Randomization

Patients will then be randomized (using an online randomizer, similar to a flip of a coin) to one of two anesthetic protocols: regional block with single dose of anesthetic versus regional block with continuous infusion using an OnQ pump. If for some reason, the anesthesiologist feels that a patient would benefit from one type of anesthesia over another, the patient will be removed from the study and given that type of anesthesia.

Intervention

Patients will be randomized to one of two anesthetic protocols: general anesthesia/sedation with a single shot, peripheral nerve block versus general anesthesia/sedation with a continuous, peripheral nerve block.

All anesthesia will be provided by an attending anesthesiologist with or without an anesthesiology resident/CRNA. Patients will have standard ASA monitors placed (pulse oximeter, blood pressure, EKG) and an intravenous line started. Sedation will be given using a combination of midazolam (1-4 mg) and fentanyl (25-100 mcg). Patients in both groups will receive an ultrasound-guided peripheral nerve block. The block will be either an infraclavicular brachial plexus block or a popliteal nerve block, depending on

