Location and type of surgical procedure, duration of procedure, and duration of intravenous sedation will also be recorded. Total time in the operating room will also be noted. Time admitted to PACU, time clinically ready for discharge, time actually discharge, PACU medications for nausea/vomiting and PACU meds for pain will all be recorded prior to discharge.

Post-operative pain will be assessed using the Visual Analogue Scale (0-100) prior to being discharged from PACU. Time to discharge and amount of pain medication taken in the PACU will be recorded.

Patients will be contacted 8 hours, 12 hours, 24 hours, 48 hours and 72hrs after surgery by the operative surgeon or research coordinator to assess their pain scale and pain medication intake. Patients will be seen for routine post-operative follow-up visits at two, six, twelve, twenty-four, and fifty-two weeks. At these times, patients will be assessed for pain, residual neurological symptoms, and signs of infection. Patients will also be asked if they were satisfied with their postoperative pain control. Total duration of study will be fifty-two weeks. Data collection documents will be distributed to the patients at time of surgery to assist in patient understanding.

Inclusion criteria

1. Patients at least 18 years old.
2. Male or Female
3. All racial and ethnic groups
4. Fractures and fracture/dislocations of the foot, ankle, tibia, fibula, elbow, forearm, wrist and hand
5. Patients who opt for surgical treatment of their fractures.
6. Patients who consent to be randomized.
7. Patients who are willing to follow-up for a minimum of 52 weeks.

Exclusion criteria

1. Patients younger than 18 years old.
2. Patients who are on chronic opioids
3. Patients who abuse opioids
4. Patients who are unwilling to follow-up for a minimum of 52 weeks.
5. Neurologic condition that could interfere with pain sensation

Characteristics of the Research Population

1. **Total number of subjects:** 100 subjects
2. **Gender:** Male or Female
3. **Racial and Ethnic Origins:** All are included

Study payments/cost:

Study participants will not incur any additional costs or payments as a result of this study. Any additional costs will be absorbed by the NYU Departments of Orthopaedics and Anesthesia

Potential Risks and Discomforts:

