Participant medical information will be stored electronically within a password protected spreadsheet available only to the PI, co-investigators, and research staff as necessary for data analysis. The names, social security numbers, and medical record numbers of the study participants will be deleted from their stored medical information and replaced with a linkage code. Access to participant medical information contained within the registry will be restricted.

Protection Against Risk: All procedures will be performed as outlined above. After the procedure pt will be contacted 6-8 hours after surgery and at 24 hours, 48 hours and 72hours after surgery by the operative surgeon or research coordinator to assess their pain scale and pain medication intake. Patients will be seen for routine post-operative follow-up visits at two, six, twelve, twenty-four, and fifty-two weeks. At these times, patients will be assessed for pain, residual neurological symptoms, and signs of infection, and starting at the six week time point, patient's functional status will be assessed using the Disability of the Arm, Shoulder and Hand (DASH) and SMFA scores, both are widely accepted and validated functional measures.

Method of Subject Identification and Recruitment: All patients seen in the outpatient office, who fit the inclusion criteria will be asked to participate in the study.

Subject/Representative Comprehension: None

Debriefing Procedures: All patients will have regular follow-up at which point, all questions regarding the study can be answered.

Documentation of Consent: A copy of the signed consent form will be securely kept for our records.

Statistical analysis plan:

A preoperative power analysis was performed. On a VAS scaled from 1-100, assuming a standard deviation of 20, the number needed to detect a 10 point change in VAS was 38. Assuming a drop out rate of 20%, we will require 50 patients in each group to determine significance. The primary end points of the study for Visual Analog Score will be assessed using two-group t-tests (Mann-Whitney U test where appropriate). Amount of pain medication utilized post operatively will be assessed using Student t-tests. Residual neurological symptoms and signs of infection will be reported as descriptive statistics. Descriptive statistics will be reported as means +/- SD for continuous variables and as frequencies and percentages for categorical variables.

References

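### No preoperative VAS is collected, so the postoperative comparison cannot adjust for initial pain: a cheap gain in precision of uncertain size, not a flaw in validity

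*Combined protocol and SAP*

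**What the plan says.** The sizing statement in the section Statistical analysis plan reads "On a VAS scaled from 1-100, assuming a standard deviation of 20", "the number needed to detect a 10 point change in VAS was 38". It continues: "Assuming a drop out rate of 20%, we will require 50 patients in each group to determine significance". No alpha, sidedness or power is given. The same section assigns the VAS to a two-group t-test, or a Mann-Whitney test where appropriate, and names no covariate.

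Under Data collection, the first pain score is postoperative: "Post-operative pain will be assessed using the Visual Analogue Scale (0-100) prior to being discharged from PACU". Further scores follow at 8, 12, 24, 48 and 72 hours and at clinic visits. The time points repeated under Data Monitoring Plan and Protection Against Risk are also all after surgery. No preoperative score is listed anywhere.

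The inclusion criteria run from foot, ankle and tibia to elbow, wrist and hand, and the Intervention section uses one of two blocks according to fracture site. Allocation is described under Randomization as "using an online randomizer, similar to a flip of a coin", with no stratification mentioned.

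The Consent section shows that patients are seen beforehand: "At the patients preoperative office visit, they will be asked to participate in the study". They are spoken to again on the day of surgery, when surgical consent is taken.

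**The concern.** Pain before the block is an obvious candidate predictor of pain afterwards. If it is never measured, it cannot be used to reduce residual variance, and nobody can see or correct a chance difference in initial pain between the arms. Neither stratification nor any planned covariate does this job in another way. The opportunity also passes for good: once the block is in, a patient's pre-treatment pain cannot be recovered.

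This matters more in a trial with little power to spare. Under conventional settings the planned comparison has about 60% power for its own target, so precision that costs almost nothing is worth having.

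The word change adds a smaller risk. Without a preoperative score it has no stated reference point. If a baseline were later added and an analyst took the word literally, raw change scores could give less power than the postoperative scores alone.

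**Working it through.** **Inputs from the documents.** Difference 10, SD 20, dropout 20%, 50 per group (Statistical analysis plan); two arms of equal planned size.

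**Assumptions, not in the documents.** Two-sided 5%; 80% as the conventional power target; SD 20 is the SD of a single postoperative score; correlation r between preoperative and postoperative VAS from 0.1 to 0.5.

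**1. The plan's own figure.** Read 38 as per group, since it is inflated to 50 per group. The normal approximation for two means is

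n per arm = 2 × (1.960 + 0.842)² × (SD/difference)² = 2 × 7.849 × 4 = 62.8, so 63; the exact t-test gives 63.8, so 64.

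The figure of 38 is not reproduced at these settings. The dropout step is acceptable: 38/0.8 = 47.5, so 48, rounded up in the plan to 50. Fifty less 20% leaves 40 analysed per arm.

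**2. Unadjusted power.** Standardized difference 10/20 = 0.5. Exact two-sided t-test power at 40 per arm is 59.8% (57.6% at 38, 69.7% at 50).

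**3. Power with preoperative VAS as covariate.** Residual SD = 20 × √(1 − r²). Equivalent gain in sample size = 1/(1 − r²) − 1. The single degree of freedom spent on the covariate is ignored.

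| r (assumed) | Residual SD | Gain in effective n | Power, 40 per arm |
|---|---|---|---|
| 0 | 20.0 | 0% | 59.8% |
| 0.1 | 19.9 | 1% | 60.2% |
| 0.2 | 19.6 | 4% | 61.6% |
| 0.3 | 19.1 | 10% | 63.9% |
| 0.4 | 18.3 | 19% | 67.4% |
| 0.5 | 17.3 | 33% | 72.2% |

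Solving for 80% power at 40 per arm gives r of about 0.62.

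**4. Why not change scores.** If the preoperative SD is also 20, the SD of a change is 20 × √(2(1 − r)): 25.3 at r = 0.2, 23.7 at r = 0.3 and 20.0 at r = 0.5. Power at 40 per arm is then 41.5%, 46.3% and 59.8%. Below r = 0.5 a change score does worse than ignoring the baseline. The plan does not propose this analysis; the figures only show why the remedy should be ANCOVA.

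**The case against.** A reader might infer from the word change that the primary endpoint is change from baseline, and that it cannot be computed because there is no baseline. The documents do not support that. The Purpose section sets out a comparison of postoperative pain control between the arms, the planned test is a two-group comparison of VAS, and no section defines a change from baseline. Change is best read as loose wording for difference. The endpoint needs no preoperative score, and randomization makes the unadjusted test valid.

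The benefit also rests on a correlation that the documents do not give. It could be low: preoperative fracture pain would be related to scores taken after surgery and after a block that both arms receive. At r = 0.1 the gain is 0.4 percentage points, and at 0.2 to 0.3 it is about 2 to 4. The power figures depend on the assumed test as well; a one-sided 5% test would have 71.6% power unadjusted at 40 per arm. No pain values by fracture site are given, so large differences between sites are plausible but not shown. Site of surgery is already recorded and could serve as a covariate with no new data.

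All of this stands, and it confines the point to an inexpensive improvement. It does not remove it: no initial pain score is planned, nothing else replaces one, and a suitable contact already exists.

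**Conclusion.** The point holds as a cheap improvement. The plan cannot adjust for initial pain, and the loss is in precision and in protection against chance imbalance, not in validity. On the stated SD and difference, an assumed two-sided 5% test and 40 analysed per arm, adjustment would raise power from 59.8% to between 60.2% and 72.2% for correlations of 0.1 to 0.5. The gain could be close to nil.

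It would be wrong to conclude that a baseline score repairs the trial's power. About 0.62 would be needed for 80%, above the range assumed here. That 38 per arm does not follow from a difference of 10 and an SD of 20 under conventional settings (about 64 needed, or 64/0.8 = 80 with dropout) is a separate problem and needs its own correction.

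**What to change.** - **Data collection:** add one VAS on the same 0-100 scale, asked before sedation and block at the existing day-of-surgery contact.
- **Statistical analysis plan:** prespecify an ANCOVA of postoperative VAS on treatment arm with preoperative VAS as covariate, and state that raw change scores will not be used. Fracture location, already recorded, can be a second covariate.
- **Power statement:** replace the 10-point change by a 10-point difference between groups, and state alpha, sidedness, power and what the SD of 20 refers to.

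The cost is one extra question per patient and one or two model terms, with no added staff or procedure. The downside is that the gain is negligible if the correlation proves low. Recalculating the sample size remains necessary whether or not this is adopted.

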2. Responsibilities and roles for gathering, evaluating and monitoring the data:
 - a. All data (including details about adverse/unexpected events) will be collected by the operative team or research coordinator at specific time points: 8hrs post-op, 24hr, 48hr, 72hrs, 2wks, 6wks, 12wks, 24wks and 52wks and reported to the research coordinator using standard templated data collection forms. All patients will be told to call [name] at [contact] to report adverse reactions during the study.
 - b. All data will be verified by the research team and coordinator for accuracy and compliance with the protocol at each time point as designated above.
3. Information about the monitoring entity:
 - a. Principle investigator [name], [name], and [name] comprise the monitoring entity.
4. Reporting Adverse events and Unanticipated problems to the monitoring entity:
 - a. The Principal Investigator will submit a Reportable Events Form for all reportable information to the IRB within 5 working days from when the Principal Investigator learns of the event or new information.
5. Assessments:
 - a. The Monitoring entity will review data monthly and assess the data for unanticipated problems involving risks to participants.
6. Criteria for Action:
 - a. Specific triggers for action include any event that is deemed to be a risk to life or limb.
7. Procedure for communicating:
 - a. The Principal Investigator will submit a Reportable Events Form for all reportable information to the IRB within 5 working days from when the Principal Investigator learns of the event or new information.

Data Storage and Confidentiality: All patients will be de-identified and given a code. Information linking the linkage codes to the participants' names, social security numbers and medical record numbers will be stored in a secure location separate from the medical information. Access to the information linking the linkage codes with participant identifiers shall be documented. The patient's informed consent will be obtained in one of the exam rooms in the private office.

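### The primary VAS comparison is undefined: no time point, summary measure, alpha or multiplicity rule is given for up to six acute pain scores

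*Combined protocol and SAP*

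**What the plan says.** The primary analysis is one sentence in the Statistical analysis plan: "The primary end points of the study for Visual Analog Score will be assessed using two-group t-tests (Mann-Whitney U test where appropriate"). End points is plural. The same paragraph sizes the trial for one unspecified VAS comparison: "the number needed to detect a 10 point change in VAS was 38", with an assumed SD of 20. It then adds: "Assuming a drop out rate of 20%, we will require 50 patients in each group to determine significance". It gives no time, alpha, sidedness or power.

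Data collection sets out the acute scores. The first is in the recovery unit: "Post-operative pain will be assessed using the Visual Analogue Scale (0-100) prior to being discharged from PACU". The rest are by telephone: "Patients will be contacted 8 hours, 12 hours, 24 hours, 48 hours and 72hrs after surgery". That makes six acute times. VAS is named only for the first; the calls are made "by the operative surgeon or research coordinator to assess their pain scale and pain medication intake", and that scale is not named.

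Two other sections list the contacts without the 12-hour call. Data Monitoring Plan, item 2a, has "8hrs post-op, 24hr, 48hr, 72hrs, 2wks, 6wks, 12wks, 24wks and 52wks". Protection Against Risk has "pt will be contacted 6-8 hours after surgery and at 24 hours, 48 hours and 72hours after surgery". On those lists there are five acute times. Pain is also assessed at five clinic visits from 2 to 52 weeks.

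The nearest hint at a key time is the 12-24 hour rebound window in Scientific or Scholarly Rationale. It is never made an endpoint.

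**The concern.** If the primary comparison is not fixed in advance, it can be chosen after the results are known. As written, a significant difference at any acute time could be reported as meeting the primary endpoint, and the usual 5% error rate would not apply to that claim.

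The times also answer different questions. Under Intervention, both arms receive the block before surgery and the pump is connected only in PACU, so the PACU score can show little of the infusion's effect. At 24 hours the infusion is running. At 48 hours the catheter is about to come out or has just done so, and at 72 hours it should be gone. If the pump arm had less pain at 24 hours but more at 72, no rule says which result answers the study question.

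The undefined condition for using Mann-Whitney adds a smaller freedom of the same kind.

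**Working it through.** **The plan's own figure.** Inputs from the Statistical analysis plan: difference 10, SD 20, so d = 10/20 = 0.5. At an assumed two-sided 0.05 and 80% power, n per arm = 2 × (1.960 + 0.842)² × (20/10)² = 62.8, so 63 (64 by the t-test). The stated 38 does not reproduce on those settings. It does match one-sided 0.05 with 70% power, but the plan states neither alpha nor power, so the sample-size sentence cannot be used to infer the intended primary test. For drop-out, 38/0.8 = 47.5, so 48, against the stated 50. Fifty per arm less 20% leaves 40 completers per arm, the number used below.

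**False-positive chance if any time counts.** Assumptions not in the plan: each of k times is tested at two-sided 0.05, any significant time counts as success, the calls use VAS, and the scores share an equal correlation ρ. With no true effect,

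P(at least one significant) = 1 − ∫ φ(u) [Φ((c − √ρ·u)/√(1−ρ)) − Φ((−c − √ρ·u)/√(1−ρ))]^k du, with c = 1.96.

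| Times tested | ρ = 0.5 | ρ = 0.7 | ρ = 0.9 | ρ = 0.95 |
|---|---|---|---|---|
| 6 (Data collection) | 20.7% | 16.4% | 10.8% | 8.9% |
| 5 (12 h omitted) | 18.3% | 14.8% | 10.2% | 8.5% |
| 11 (adding 2-52 weeks) | 30.4% | 22.3% | 13.1% | 10.3% |

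Independent scores would give 1 − 0.95⁶ = 26.5% for six times, but independence within a patient is implausible. Simulated t-tests with 40 per arm agree with the six-time row. If correlation decays with separation in the visit sequence (first-order autoregressive, adjacent correlation 0.5, 0.7, 0.9), six times give 23.7%, 20.0% and 13.3%.

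**Adding the choice of test.** If the better of the t-test and Mann-Whitney could be taken at each time, simulation with normal data gives about 24%, 19%, 13% and 11% for six times at ρ = 0.5, 0.7, 0.9 and 0.95. A single time gives about 6%.

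**Power of one pre-specified test.** With d = 0.5 and two-sided 0.05, t-test power is 59.8% at 40 per arm and about 80% at 63-64. The 95% confidence interval half-width at 40 per arm is 1.991 × 20 × √(2/40) = 8.9 points.

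**Power of a mean over several calls.** The SD of a mean of m scores is 20 × √((1 + (m−1)ρ)/m). With 40 per arm, over ρ = 0.95 to 0.5:

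| Calls averaged | SD of the mean | 10 points at every call | No effect at one call |
|---|---|---|---|
| 8, 12, 24, 48 h | 19.6 to 15.8 | 61% to 80% | 39% to 55% (mean effect 7.5) |
| 8, 24, 48 h | 19.7 to 16.3 | 61% to 77% | 32% to 44% (mean effect 6.7) |

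**Keeping all six as alternatives.** Bonferroni gives 0.05/6 = 0.0083 per test. Eighty per cent power at one time then needs 97 per arm, or 97/0.8 = 121.25, so 122 with drop-out. Forty completers per arm would have about 34% power at a single time.

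**The case against.** The strongest reply is that the inflation is hypothetical. The plan does not say that each time will be tested at 0.05 or that any one suffices. Read literally, VAS attaches only to the PACU score, which would leave one time and no multiplicity over times. The count of six is itself a choice, because the clinic visits also record pain and two contact lists omit 12 hours. Equal correlation is an assumption too, so 11-21% is not a bound.

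Much of this stands as a limit on the figure: it is conditional and should be quoted with its conditions. It does not remove the defect. The literal reading sits badly with the plural end points, and it would make primary the one score that can show little of the infusion's effect. Restricting the count to acute times follows the stated purpose of comparing post-operative pain control; adding the clinic visits or letting correlation decay raises the rates. Dropping the 12-hour call lowers them only slightly, and even ρ = 0.95 gives 8-9%.

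Nor does the 12-24 hour window serve as an implied primary time: the rationale uses it to describe blocked against unblocked patients, whereas both arms here are blocked.

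It is also fair to say that 60% power is a separate sample-size weakness. Naming one primary time does not cause it, but makes it visible.

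**Conclusion.** The concern holds. No section defines which VAS comparison is primary, at what alpha, or by which of the two tests, and no redaction accounts for the gap. That conclusion rests on the text alone and is firm.

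The size of the harm is conditional. With two-sided 0.05 at each time, any time counting, VAS used at the calls and equal correlation of 0.5 to 0.9, the false-positive chance is about 21% to 11% for six times, or 18% to 10% for five. The correlation range is assumed.

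This must be fixed before outcomes are compared between arms. Without a defined primary comparison, a significant result cannot be read as confirmatory, and the sample size is not tied to any particular test. Choosing the time after seeing the results would not repair that.

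**What to change.** State alpha and sidedness, name one primary VAS comparison and one test, and make every other time secondary. Possible wording:

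> The primary endpoint is VAS at 24 hours after surgery, compared between arms once by a two-group t-test at two-sided 0.05. VAS at all other times is secondary and is reported as mean differences with 95% confidence intervals. A Mann-Whitney test of the 24-hour score is a sensitivity analysis only.

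The 24-hour score is one defensible choice: it appears in all three contact lists and lies in the rebound window that motivates the trial, although the infusion is still running then. A single pre-specified mean over named acute calls is another. The investigators should choose. The plan should also state that VAS is the scale used at the calls and reconcile the 12-hour contact across Data collection, Data Monitoring Plan and Protection Against Risk, especially if a mean is to include that call.

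The change is to wording only, but it has a price. Success can no longer be claimed at whichever time is significant. A 24-hour primary leaves pain after catheter removal as secondary. A mean loses power if one of its calls shows no effect. The plan should state that one test at 40 completers per arm has about 60% power for 10 points, and that 80% needs about 63-64 completers per arm.

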the location of the fracture. The appropriate region will be prepped with a chlorohexidine solution on the appropriate surgical side and the appropriate site will be visualized under ultrasound. For the group receiving a single shot block, a 22 gauge, 3.5 inch needle will be used and 20cc of 2% lidocaine with 1:200,000 epinephrine + 20 cc of 0.5% bupivacaine with 1:300,000 epinephrine will be injected around the nerve after confirming negative aspiration every 5 cc. For those receiving a continuous infusion, a 17 gauge Tuohy needle will be used and 20cc of 2% lidocaine with epinephrine + 20 cc of 0.5% bupivacaine with 1:300,000 epinephrine will be injected around the nerve after confirming negative aspiration every 5cc. Once the injection is complete, an indwelling catheter will be placed with its tip location confirmed and then secured at the skin.

After placement of the regional block, general anesthesia/sedation will be administered and maintained at the discretion of the anesthesiologist. Induction of anesthesia will involve IV propofol (2mg/kg) and fentanyl (1-2mcg/kg). Neuromuscular blockade will be used at the discretion of the anesthesiologist and will be reversed appropriately. Anesthetic maintenance will involve inhalational agents, IV agents, air, and oxygen. Fentanyl will be the only intraoperative analgesic used and will be dosed as determined by the anesthesiologist.

After completion of the surgery, patients will be taken to the PACU where those with continuous catheters will have an OnQ pump attached to it. The patient will begin receiving a continuous infusion of 0.2% ropivacaine through the catheter at a rate of 8 cc/hr. The patient will be discharged home with the catheter for 48 hours. The study participant will self-discontinue the catheter in 2 days. This involves removing the tegaderm dressing and gently pulling the catheter out from under the skin. A bandage may then be applied. [name], our anesthesiology RN, will be available via phone to answer any questions study participants may have regarding discontinuation of the catheter. Breakthrough pain while in the PACU will be treated with IV fentanyl and PO Percocet as needed.

Postoperatively, all patients will be discharged home with a prescription for Percocet 5/325 with instructions to take 1-2 tabs every 4-6hrs as needed for pain.

Data collection

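### VAS is compared between arms without a limb term; prespecifying one is a cheap, optional gain in precision that the documents do not allow to be sized

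*Combined protocol and SAP*

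**What the plan says.** - **Analysis** (Statistical analysis plan): "The primary end points of the study for Visual Analog Score will be assessed using two-group t-tests (Mann-Whitney U test where appropriate". This is the only analysis given for VAS. No section adds a covariate, a stratified test or a comparison by limb.
- **Sample size** (same section): "assuming a standard deviation of 20, the number needed to detect a 10 point change in VAS was 38", and then "Assuming a drop out rate of 20%, we will require 50 patients in each group to determine significance". The plan does not say whether the SD is pooled over limbs or applies within a limb.
- **Block** (Intervention): "Patients in both groups will receive an ultrasound-guided peripheral nerve block". Further, "The block will be either an infraclavicular brachial plexus block or a popliteal nerve block", the choice depending on "the location of the fracture".
- **Population** (Inclusion criteria): "Fractures and fracture/dislocations of the foot, ankle, tibia, fibula, elbow, forearm, wrist and hand". Both limbs are eligible, and the fracture site is known at enrolment.
- **Recording** (Data collection): "Location and type of surgical procedure, duration of procedure, and duration of intravenous sedation will also be recorded". Block site is not itself listed as recorded, but limb follows from the procedure location.
- **Allocation** (Randomization): an online randomizer likened to a coin flip, with no stratification by limb.

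**The concern.** The trial combines two anatomical regions and two block sites in one comparison, and handles limb neither in the randomization nor in the analysis. If mean VAS differs between limbs, an unadjusted comparison leaves that difference in the error variance. Chance imbalance in limb mix between arms then moves the estimate: with a 10-point limb gap, a limb share that differs by 10 percentage points between arms shifts the unadjusted difference by 0.10 x 10 = 1 VAS point. Such imbalance is common. At 40 per arm and a 50:50 mix, the SD of the difference in limb share is sqrt(2 x 0.25/40) = 0.112, so a difference of 10 percentage points or more arises in about 37% of trials.

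At stake is the width of the interval for the arm difference. There is also the question of whether any adjustment for limb is fixed in advance or chosen after a visible imbalance.

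**Working it through.** **Inputs from the plan.** SD 20, difference 10 VAS points, 50 enrolled per arm, 20% dropout, so 100 x 0.80 = 80 evaluable.

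**Assumptions, because the documents are silent.** Two-sided 0.05, normal data, no arm-by-limb interaction, limb gap g of 0 to 20 VAS points, share p in the larger limb group of 50% to 90%.

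**1. The plan's own figure.** For two groups at two-sided 0.05 and 80% power, n per arm = 2 x (1.960 + 0.842)^2 x 20^2/10^2 = 63, not 38. A value of 38 per arm does come out at one-sided 0.05 with 70% power, but the plan states neither. The dropout step is acceptable: 38/0.80 = 47.5, so 48, against 50. With 40 evaluable per arm the unadjusted t-test has 59.8% power (noncentral t). This shortfall is a separate matter; here it only sets the baseline.

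**2. What a limb term does.** If SD 20 is pooled over limbs, the residual SD after removing limb is sqrt(400 - p(1-p)g^2). Against this, coin-flip allocation leaves some chance correlation between arm and limb, with mean square of about 1/79 for 80 patients. That multiplies the standard error by about 1/sqrt(1 - 1/79) = 1.006. Normal-approximation power is Phi(10/SE - 1.96):

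- No limb term: SE = 20 x sqrt(2/40) = 4.47; 10/4.47 = 2.236; power 60.9%.
- Limb term, gap 0: SE = 4.50; ratio 2.222; change -0.5 points.
- Limb term, gap 10, 50:50: residual SD 19.36; SE 4.36; ratio 2.295; change +2.2.
- Limb term, gap 20, 50:50: residual SD 17.32; SE 3.90; ratio 2.566; change +11.9.
- Limb term, gap 10, 90:10: residual SD 19.77; SE 4.45; ratio 2.247; change +0.4.

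**3. Simulation.** 60,000 trials per scenario, arm by coin flip; t-test on 78 df against a linear model with arm and limb on 77 df. The Monte Carlo SE is about 0.2 points per power figure. Unadjusted power is about 59%. Change in power, in points, with SD 20 pooled over limbs:

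| Limb mix | Gap 0 | 5 | 10 | 15 | 20 |
|---|---|---|---|---|---|
| 50:50 | -0.5 | +0.1 | +2.2 | +5.9 | +11.9 |
| 70:30 | -0.7 | 0.0 | +1.7 | +4.9 | +9.7 |
| 80:20 | -0.5 | -0.2 | +1.1 | +3.5 | +6.9 |
| 90:10 | -0.6 | -0.4 | +0.4 | +1.8 | +3.4 |

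The closed form in step 2 agrees. At 50:50 the simulated SE of the arm difference falls from 4.49 to 4.38 at a 10-point gap and from 4.49 to 3.93 at 20.

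**4. Other reading of the SD.** If SD 20 applies within limb, adjusted power stays near 59% and unadjusted power falls as the gap grows. At 50:50 the gains are 0.0, +2.2, +5.0 and +8.5 points for gaps of 5, 10, 15 and 20; at 90:10 they are -0.2, +0.4, +1.5 and +3.2.

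**5. Validity.** With no arm effect, type I error is 4.8% to 5.2% with or without the limb term.

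**6. Rank version.** A van Elteren test stratified by limb, against Mann-Whitney with pooled SD, changes power by about -0.9 to -1.0 points at gap 0 and by -0.5 to -0.7 at gap 5 (mixes 50:50, 80:20 and 90:10).

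**The case against.** An unadjusted two-group test under simple randomization is an accepted and valid choice. No section says that VAS differs between upper and lower limb, or between the two blocks. Intervention says only that fracture location sets the block site, and the discussion of rebound pain in the rationale does not separate limbs. The limb mix is unknown too, and Potential Benefits speaks of evidence on forearm and wrist fractures, so one limb might dominate. For limb gaps no larger than the trial's own 10-point target the gain is at most about 2 points and can be slightly negative. The simulations use unbounded normal data and no arm-by-limb interaction, whereas VAS is bounded and the two limbs receive different blocks.

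All of this stands. It limits the point to an optional improvement. It does not remove it, because the possible loss is small and the covariate is already in the planned data.

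A reader might go further and infer that the planned test is wrong or biased. It is not: it holds its type I error, and chance imbalance in limb mix is random error that its standard error already covers. A reader might also infer that a stratified rank test should replace Mann-Whitney. The figures do not support that: it loses up to about 1 point when the limb gap is 5 points or less, and it gives no interval for the arm difference.

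**Conclusion.** The point holds as a cheap, optional improvement, not as an error. A factor fixed before randomization, obtainable from planned data and tied to the choice of block is left out of the VAS comparison. With 80 evaluable patients, SD 20 pooled over limbs, a 10-point effect, two-sided 0.05 and mixes from 50:50 to 90:10, a limb term changes power by about -0.7 to +2.2 points for gaps of 0 to 10 and by about +2 to +12 for gaps of 15 to 20. Which range applies cannot be read from the documents, since they give neither VAS by limb nor the expected mix.

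Two inferences go too far. The upper figure of 12 points is not an expected gain: it needs an even mix and a limb gap twice the target effect, which nothing in the plan suggests. Nor does the term repair the sample size: the highest adjusted power in any scenario is about 71%.

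**What to change.** Before outcomes are seen by arm, add to the Statistical analysis plan, for example:

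> The main comparison of VAS between arms will use a linear model with arm and limb (upper: hand, wrist, forearm, elbow; lower: tibia, fibula, ankle, foot). Limb is coded from the location, known before randomization, of the fracture treated in the study surgery, not from the block given. The arm coefficient with its 95% CI is the result. The unadjusted two-group test is a sensitivity analysis.

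A further line should say how a patient operated on in both limbs is coded. A van Elteren test stratified by limb may be listed as another sensitivity analysis but need not be. The model applies at whichever VAS time point is analysed; naming the primary time point is a separate matter.

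The cost is one derived variable, one model term and one degree of freedom, with no added patients or data. If limb is unrelated to VAS, about 0.5 to 0.7 power points are lost.
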